### **13.3 Patient Disposition**

A detailed description of patient disposition will be provided. It will include:

- A definition of patient enrollment
- A summary of data regarding patient discontinuation of study treatment
- A summary of data regarding patient inclusion and exclusion in efficacy and safety analyses

### **13.4 Patient Characteristics**

Patient characteristics will include a summary of the following:

- Patient demographics
- Baseline disease characteristics
- Baseline tumor molecular characteristics
- Significant medical history and co-morbidities
- Concomitant therapies
- Other characteristics as appropriate

### **13.5 Safety of Treatment**

A summary of the adverse events and their attributed relatedness to treatment will be provided. All patients will be included in the safety analyses

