### 6.2.3 Surveillance for Cardiac Toxicities

In telemetry studies in monkeys, no clear effects on the QTc interval have been observed following administration of AUY922. But based upon *in vitro* and *in vivo* data, a potential for cardiovascular toxicity, such as QTc prolongation or proarrhythmia with AUY922 could not be excluded; therefore, cardiovascular monitoring will be conducted throughout the study.

As part of the screening process, patients will be required to undergo either a MUGA or transthoracic echocardiogram to assess left ventricular ejection fraction (LVEF). Patients will be closely monitored by ECG throughout the study, see schedule below. If cardiac changes are observed during monitoring, please refer to Section 6.3 for dose modifications.

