| Grade 3 (>5.0 - 20.0 x ULN )  | Omit dose administration until resolved to ≤ grade 1 (or ≤ grade 2 in case of liver metastasis), then 

• If resolved in ≤ 7 days, then maintain dose level

• If resolved in > 7 days, then decrease by 1 dose level

   |
| Grade 4 (> 20.0 x ULN)  | Omit dose administration until resolved to ≤ grade 1, then decrease by 1 dose level   |
| Cardiac - Prolonged QTcF interval  |   |
| During cycle 1  |   |
| Absolute QTcF ≤ 480msec   | Maintain dose level and ECG monitoring as per visit schedule.   |
| Absolute QTcF ≥ 481msec and, ≤ 500 msec   | Maintain dose level. ECG monitoring assessments should be performed for 2 additional cycles at the same frequency as in cycle 1. After the second additional cycle, ECGs for subsequent cycles will be performed as follows: 

• If ECG in the additional cycles shows no QTcF absolute ≥ 481 msec then, for subsequent cycles ECG monitoring will be performed as per visit schedule.

• If ECG still abnormal (QTcF absolute ≥ 481 msec and ≤ 500 msec) then ECG monitoring must continue at the same frequency as in cycle 1 for all subsequent cycles.

 |

| Recommended Dose Modifications for AUY922  |  |
|---|--|
| Worst Toxicity
CTCAE Grade a. unless otherwise
specified                | At any time during a cycle of AUY922
(including intended day of dosing)   |

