| Survival   |                |         |   |   |         |    |   |                   |    |                 |                  |                     | X                     | X                         | X            |     |
| Tumor sample for mutation and amplification testing  | X              |         |   |   |         |    |   |                   |    |                 |                  |                     | X                     | X                         | X            |     |

1. Vital signs – During treatment period, vital signs will be performed pre-dose (including temperature, respiratory rate, blood pressure, pulse, weight and ECOG PS) and immediately post-dose infusion (including temperature, respiratory rate, blood pressure and pulse).
2. ECG- Please refer to Table 3 for detailed schedule of ECGs.
3. In women of child-bearing potential, a serum pregnancy test must be obtained prior (within 14 days) to the first administration of AUY922. CHEMISTRY: BUN, Creatinine, Glucose, Total Protein, Albumin, AST/SGOT, ALT/SGPT, Total Bilirubin, Alkaline Phosphatase, Magnesium, Calcium, Sodium, Potassium, Phosphorous. HEMATOLOGY: CBC with differential
4. Standard ophthalmologic assessments will be required at baseline and follow-up exams will be conducted at the time when visual symptoms are reported (if any), at cycle 3 day 1 if no visual symptoms are reported, and at study discontinuation. There is a +/- 7 day window allowed for eye exam at Cycle 3 day 1
5. One should aim to administer AUY922 on the same day each week, but there is a +/- 2 day window allowed to account for holidays, inclement weather, transportation difficulties, etc. For patients who are unable to tolerate the protocol-specified dosing schedule, schedule adjustments are permitted. This includes the ability to skip a week of dosing if needed up to once per cycle. Patients who continue treatment beyond progression can skip up to two infusions per cycle if needed after discussion between the treating MD and the overall PI of the study.
6. A CT scan with contrast of the chest, abdomen, and pelvis will be performed on patients at baseline (screening) -30 to -1 days prior to study drug administration. The same type of imaging modality (CT with contrast or MRI) used at screening must be used for all subsequent follow-up assessments. Follow-up CT/MRI scans will be performed every 6 weeks ( $\pm$ 7 days) from registration.

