## 10. ADVERSE EVENT REPORTING REQUIREMENTS

### 10.1 Definitions

#### 10.1.1 Adverse Event (AE)

An adverse event (AE) is any undesirable sign, symptom or medical condition or experience that develops or worsens in severity after starting the first dose of study treatment or any procedure specified in the protocol, even if the event is not considered to be related to the study.

Abnormal laboratory values or diagnostic test results constitute adverse events only if they induce clinical signs or symptoms or require treatment or further diagnostic tests.

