## 10.2 Procedures for AE and SAE Recording and Reporting

Reporting Participating investigators will assess the occurrence of AEs and SAEs at all participant evaluation time points during the study.

All AEs and SAEs whether reported by the participant, discovered during questioning, directly observed, or detected by physical examination, laboratory test or other means, will be recorded in the participant's medical record and on the appropriate study-specific case report forms.

The descriptions and grading scales found in the CTEP NCI Common Terminology Criteria for Adverse Events (CTCAE) version 4.0 will be utilized for AE reporting, and can be found on the CTEP website at:

[http://ctep.cancer.gov/protocolDevelopment/electronic\\_applications/ctc.htm](http://ctep.cancer.gov/protocolDevelopment/electronic_applications/ctc.htm).

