# 13. STATISTICAL CONSIDERATIONS

## 13.1 Study Design/Endpoints

The primary purpose of this study is to determine the efficacy of AUY922 when administered intravenously on a once-weekly schedule at 70 mg/m^2 in adult NSCLC patients with advanced disease and EGFR exon 20 insertion mutations. The design will be a Simon two-stage phase 2 study, with 10 patients enrolled to the first stage and an additional 19 patients enrolled to the second stage provided we observe at least 1 partial or complete response or stable disease lasting  $\geq 3$  months in the first stage.

The Primary Objective is:

- To evaluate the overall response rate to AUY922 in patients with advanced NSCLC and exon 20 insertion mutations in *EGFR*.

Secondary Objectives include:

- To estimate progression-free survival (PFS) and overall survival (OS) in the study population
- To determine the safety and tolerability of AUY922
- To explore variance in clinical outcome between different types of exon 20 EGFR mutations

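### Section 13.5 plans no summary of QTcF, LVEF or eye-exam results, so changes that cause no symptoms and prompt no treatment or further test have no planned report

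*Combined protocol and SAP*

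**What the plan says.** Safety is a secondary objective in sections 1.3 and 13.1: "To determine the safety and tolerability of AUY922". Section 13.5 answers it in two sentences. The first is "A summary of the adverse events and their attributed relatedness to treatment will be provided"; the second includes all patients in the safety analyses.

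Section 10.1.1 decides which test results can enter that summary: "Abnormal laboratory values or diagnostic test results constitute adverse events only if they induce clinical signs or symptoms or require treatment or further diagnostic tests". Section 10.2 covers AEs "directly observed, or detected by physical examination, laboratory test or other means, will be recorded" on the case report forms, but a result must first qualify as an AE under 10.1.1.

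The protocol gives its reasons for monitoring. Section 6.2.3 says that "a potential for cardiovascular toxicity, such as QTc prolongation or proarrhythmia with AUY922 could not be excluded", and section 6.1 concludes that QTc prolongation and visual changes may be risks. Table 3 schedules three baseline ECGs, then ECGs before and after every infusion, and at about 24 and 48 hours after the first. LVEF is measured at screening and, as far as the layout of Table 6 can be read, once more at end of treatment. Section 6.2.2 requires a five-part eye exam at baseline and when symptoms are reported. Table 6, footnote 4, adds an exam "at cycle 3 day 1 if no visual symptoms are reported, and at study discontinuation".

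**The concern.** A drug effect on QTcF would show first as a shift from each patient's baseline and as movement between categories. Symptomatic events would be a late and insensitive sign. An AE table picks up only results that crossed an action limit or that an investigator chose to act on. A team that follows 10.1.1 and 13.5 exactly could therefore issue a safety report with few or no QTc entries while QTcF rose in many patients. The three baseline ECGs suggest that change from baseline was meant to be measurable, but no section uses them for that, and Table 5 works on absolute limits only.

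The eye data raise the same question more mildly. The cycle 3 exam is scheduled for patients who report no visual symptoms, so its findings are among the least likely to become AEs.

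At stake is how completely the secondary safety objective is answered. The primary endpoint and its decision rule are not affected.

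**Working it through.** **The plan's own figure.** The plan gives no number on this point. Its only design calculation is the pair of error rates in section 13.2. With 10 then 19 patients, continuing on at least 1 success and succeeding on at least 4, P(success) = sum over x = 1 to 10 of P(X1 = x) × P(X2 ≥ 4 − x). At rates of 0.05 and 0.20 this gives a type I error of 0.0468 (stated 0.047) and a type II error of 1 − 0.8011 = 0.1989 (stated 0.199). Both reproduce, and nothing below changes them.

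**Which symptom-free results reach the AE summary.** This sets 10.1.1 against Table 5 and section 6.2.

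| Result without symptoms | What the protocol requires | Reaches the AE summary? |
|---|---|---|
| QTcF 480 msec or less, cycle 1 | "Maintain dose level and ECG monitoring as per visit schedule" | No, unless the investigator treats or tests further |
| QTcF 481-500 msec, cycle 1 | Cycle 1 ECG frequency for two more cycles | Arguably yes: further tests |
| QTcF 481-500 msec, first seen after cycle 1 | No rule; the row sits under a cycle 1 heading | No, with the same exception |
| QTcF 501 msec or more, any cycle | Hourly ECGs and a search for other causes | Yes |
| LVEF fall | Table 5's cardiac rows cover QTcF only | Only if it is treated or investigated |
| Eye finding, Grade 2 or worse | Dose omission, and permanent discontinuation at Grade 4; up to Grade 3, until recovery to Grade 1 or baseline | In practice yes up to Grade 3: showing recovery needs a repeat exam |
| Eye finding, Grade 1 or minor | Dose level kept | No, with the same exception |

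Table 5 mentions 481-500 msec in one other place, for patients already re-treated after a value of 501 msec or more.

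**Data collected.** From Table 3, cycle 1 has 2 + 1 + 1 + 2 + 2 = 8 ECGs (days 1, 2, 3, 8 and 15), and each later cycle has 3 × 2 = 6. Over four cycles (an assumption) with no missed doses, a patient has 3 + 8 + 3 × 6 = 29 ECGs. For 29 patients that is 29 × 29 = 841 at most.

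**Room below the limits.** Section 3.2.11 excludes a screening QTcF of 450 msec or more, so the highest whole-number entry value is 449. Before Table 5 requires a new test, that patient can rise 480 − 449 = 31 msec in cycle 1, or 500 − 449 = 51 msec in later cycles.

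**How few crossings a real shift might give.** The documents give no QTcF distribution, so this is illustrative. Assume a normal QTcF with baseline mean m of 405 to 425 msec, SD of 15 to 25 msec, and a mean rise of 20 msec. On a single reading, P(481 or more) = 1 − Φ((480.5 − m − 20)/SD).
- m = 405, SD = 15: z = 55.5/15 = 3.70, P = 0.0001, about 0 of 29 patients.
- m = 425, SD = 25: z = 35.5/25 = 1.42, P = 0.0778, 29 × 0.0778 = 2.3 patients.

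Repeated readings would give more crossings. Truncation at entry, ignored here, would give fewer.

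**What 29 patients can show.** If none of 29 falls in a category, the one-sided 95% upper limit is 1 − 0.05^(1/29) = 9.8%, and the upper end of the exact two-sided 95% interval is 1 − 0.025^(1/29) = 11.9%. For a mean change, the 95% half-width t(0.975, 28) × SD/√29 is 3.8, 5.7 or 7.6 msec for an assumed SD of change of 10, 15 or 20 msec.

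**The case against.** The strongest reply is that the plan is silent rather than defective. The measurements are taken, nothing forbids summarising them, and the clearest outliers already reach the AE table. Section 5.1.2 has a clinician check the ECG for QTcF above 500 msec before dosing, and the monitoring committee can ask for more information. The trial is small, has one arm, and treats safety descriptively. Without a control, and with entry capped on QTcF, some rise is expected from regression to the mean. Pre-infusion timing is expressly unspecified and no time is given for most post-infusion ECGs, so no table could settle whether AUY922 prolongs QTcF.

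Much of this stands and limits the point. A reader might infer that 10.1.1 shuts out every symptom-free result. It does not, because a need for treatment or further tests is enough. A reader might also infer that LVEF is followed serially for a stated risk. It is measured once at screening and apparently once later, and an LVEF fall is not named separately from general cardiovascular toxicity. Nor do the documents call QTc prolongation a known effect. The signal was in vitro, with no QTc effect in dog or monkey telemetry.

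The reply does not remove the gap. Dosing checks protect the individual patient but are not an analysis. Committee access on request is not a reporting commitment. Table 8 names no ECG, LVEF or eye form; the contents of the forms are not shown, so capture is neither excluded nor assured. Summaries chosen after the data are seen are also open to selection.

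**Conclusion.** The point holds in limited form and should be fixed. Section 13.5 commits to no summary of QTcF, LVEF or eye-exam values, and no other section fills the gap. The unreported region is QTcF rises ending at 480 msec or less, 481-500 msec first seen after cycle 1, an LVEF fall without symptoms or action, and minor symptom-free eye findings. For QTcF that leaves at least 31 msec (cycle 1) or 51 msec (later cycles) of possible rise. Under the assumed distributions, a 20 msec mean rise would put only about 0 to 2.3 of 29 patients at 481 msec or more on one reading.

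It would go too far to say that such changes would not be reported. The documents support only that no report is planned. The conclusion rests on the plain reading of 10.1.1 and of the cycle 1 heading in Table 5, and on a partly broken calendar for the second LVEF value. The design's error rates and primary decision are unaffected.

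**What to change.** Add a paragraph to section 13.5 with three descriptive summaries of results already obtained.

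1. **QTcF.** Report the maximum change from the mean of the three baseline ECGs. Report the number and percent, with exact 95% confidence interval, of treated patients by worst post-baseline value, using the protocol's cut-offs: 450 or less, 451-480, 481-500, and 501 msec or more. Show pre- and post-infusion values separately. The pre-infusion ECG on cycle 1 day 1 precedes any drug and should not count as post-baseline. A maximum tends to grow with the number of readings, so give the number of ECGs per patient beside it. State that the changes are uncontrolled.
2. **LVEF.** Report the paired change from baseline to the end-of-treatment value where both exist, with the number of pairs.
3. **Eye.** Report a baseline-to-worst shift table of the protocol's Snellen grade, and counts of new abnormal findings on the other required tests, including the cycle 3 exam.

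Confirm that the eCRFs in Table 8 capture these values, and add fields if they do not.

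The cost is one paragraph, three tables and some data entry. No test, visit or patient is added, and no dosing or monitoring rule changes.

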### **13.6 Analysis of Response Rate**

Response rate will be assessed as per RECIST, see Section 9.1. Results will be reported with 95% confidence intervals. All patients will be evaluable for response rate.

### **13.7 Analysis of Progression-Free and Overall Survival**

Progression-Free Survival (PFS) will be defined as the duration of time from start of treatment to time of objective disease progression or death. Overall survival (OS) will be defined as the duration of time from start of treatment until death. Analysis will be performed using the Kaplan-Meier method. All patients will be evaluable for survival endpoints.

## **14. PUBLICATION PLAN**

At the end of the study, the results will be analyzed and a manuscript submitted for peer review within 24 months of the end of data collection.

## 16. APPENDICES

### Appendix A: Performance Status Criteria

| ECOG Performance Status Scale |   | Karnofsky Performance Scale |  |
|-------------------------------|---|-----------------------------|--|
| Grade                         | Description   | Percent                     | Description  |
| 0                             | Normal activity. Fully active, able to carry on all pre-disease performance without restriction.  | 100                         | Normal, no complaints, no evidence of disease.                                 |
|                               |   | 90                          | Able to carry on normal activity; minor signs or symptoms of disease.          |
| 1                             | Symptoms, but ambulatory. Restricted in physically strenuous activity, but ambulatory and able to carry out work of a light or sedentary nature (e.g., light housework, office work). | 80                          | Normal activity with effort; some signs or symptoms of disease.                |
|                               |   | 70                          | Cares for self, unable to carry on normal activity or to do active work.       |
| 2                             | In bed < 50% of the time. Ambulatory and capable of all self-care, but unable to carry out any work activities. Up and about more than 50% of waking hours.                           | 60                          | Requires occasional assistance, but is able to care for most of his/her needs. |
|                               |   | 50                          | Requires considerable assistance and frequent medical care.                    |
| 3                             | In bed >50% of the time. Capable of only limited self-care, confined to bed or chair more than 50% of waking hours.   | 40                          | Disabled, requires special care and assistance.                                |
|                               |   | 30                          | Severely disabled, hospitalization indicated. Death not imminent.              |
| 4                             | 100% bedridden. Completely disabled. Cannot carry on any self-care. Totally confined to bed or chair.   | 20                          | Very sick, hospitalization indicated. Death not imminent.                      |
|                               |   | 10                          | Moribund, fatal processes progressing rapidly.                                 |
| 5                             | Dead.   | 0                           | Dead.  |
